**7.1.4.2.3 Day 8, Day 15, and Day 22 of Course 1**

The observations, examinations, and evaluations listed below will be conducted, and the dates of the conduct and data obtained will be documented in the medical records and CRF.

Clinical Symptoms	Subjective symptoms and objective findings
Vital Signs	Blood pressure (systolic/diastolic), pulse rate, and body temperature
Hematology Test	Hb, Hct, RBC count, WBC count, differential WBC count (visual count: blast cells [leukemia cells], lymphoblastoid cells, monoblasts, promyelocytes, myelocytes, metamyelocytes, segmented neutrophils, stab leucocytes, lymphocytes, eosinophils, monocytes, basophils, prolymphocytes, and promonocytes), platelet count, and reticulocytes
PD evaluation	Blood sampling

**7.1.4.2.4 Day 29 of Course 1**

The observations, examinations, and evaluations listed below will be conducted, and the dates of the conduct and data obtained will be documented in the medical records and CRF.

Clinical Symptoms	Subjective symptoms and objective findings
Pregnancy Test a	Urinary or serum HCG
Vital Signs	Blood pressure (systolic/diastolic), pulse rate, and body temperature
Body Weight	Body weight
Twelve-lead ECG and chest X-ray	Twelve-lead ECG and chest X-ray
Hematology Test	Hb, Hct, RBC count, WBC count, differential WBC count (visual count: blast cells [leukemia cells], lymphoblastoid cells, monoblasts, promyelocytes, myelocytes, metamyelocytes, segmented neutrophils, stab leucocytes, lymphocytes, eosinophils, monocytes, basophils, prolymphocytes, and promonocytes), platelet count, and reticulocytes
Blood Biochemistry Test	AST (GOT), ALT (GPT), ALP, LDH, TP, ALB, T-Bil, BUN, UA, Cr, blood glucose (fasting), Ca, Mg, Na, K, and Cl
Urinalysis	Bilirubin, occult blood, protein, and urobilinogen
General Condition	ECOG PS
Bone Marrow Aspiration	Percentage of bone marrow fluid (blasts, lymphoblasts, monoblasts, promyelocytes, myelocytes, metamyelocytes, segmented neutrophils, stab leucocytes, lymphocytes, eosinophils, monocytes, basophils, normoblasts, pronormoblasts, erythroblasts, plasma cells, and megakaryocytes), M/E ratio, and cellularity
PD Evaluation	Blood sampling

HCG = Human chorionic gonadotropin

a A pregnancy test will be performed in female subjects at the trial site. However, a pregnancy test is not required for subjects who have undergone bilateral oophorectomy or hysterectomy, or subjects who have been amenorrheic without a medical cause for at least 12 consecutive months.

Prior to transition to Course 2, it will be assessed when to start Course 2 and which regimen (10-day regimen or 5-day regimen) to use in reference to [Section 6.1 Dose, Regimen, and Treatment Period](#).

Written informed consent (using written information for subjects) to extended treatment in Course 2 and subsequent courses will be obtained from subjects who wish to continue to receive the treatment and are eligible for extended treatment in the opinion of the investigator or subinvestigator (between Day 22 of Course 1 and the start of Course 2). In principle, each course should consist of 28 days, and if the examination scheduled for Day 29 is performed between Day 26 and Day 28 for example, which is within the acceptable window, IMP administration for the next course should be started on or after Day 29 of the current course.

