## 6 Trial Design

### 6.1 Dose, Regimen, and Treatment Period

The total daily dose will be determined based on the subject's body surface area (BSA) calculated from height and weight prior to administration in each course, according to the treatment cohort.

SGI-110 will be administered SC at the determined daily dose after being reconstituted using the custom diluent provided.

In Cohorts 1, 2, and 4, subjects will receive SGI-110 once daily for 5 consecutive days (Day 1 to Day 5), followed by a 23-day non-dosing period (Day 6 to Day 28). One course will consist of 4 weeks (28 days). In Cohort 3, subjects will receive SGI-110 once daily for 10 days in total (SGI-110 will be administered for 5 consecutive days [Day 1 to Day 5], suspended for 2 days [Day 6 and Day 7], then administered for another 5 consecutive days [Day 8 to Day 12]), and the dosing will be suspended for 16 days (Day 13 to Day 28). One course will consist of 4 weeks (28 days).

The dose and regimen for each cohort is as follows:

Cohort 1 ( $36 \text{ mg/m}^2$ , 5-day administration)

Cohort 2 ( $60 \text{ mg/m}^2$ , 5-day administration)

Cohort 3 ( $60 \text{ mg/m}^2$ , 10-day administration [ie, 5-day administration twice, with a non-dosing period in-between])

Cohort 4 ( $90 \text{ mg/m}^2$ , 5-day administration)

SGI-110 for injection, 100 mg contains SGI-110 equivalent to 100 mg of free acid, as a lyophilized powder in a 5-mL glass vial. Subjects who complete IMP administration and all observations during the DLT evaluation period, and who do not have any apparent progression of AML, will be permitted to continue treatment with IMP following the DLT evaluation period if they wish, and will receive treatment according to the same dosing schedule as Course 1 (Cohorts 1, 2, and 4).

In Cohort 3, subjects will receive SGI-110 for 10 days in Course 1 (DLT evaluation period), for 10 or 5 days in Course 2 (Extended treatment period), for 5 days in Course 3 and subsequent courses. The investigator will determine whether or not the transition to Course 2 should be postponed and which regimen is used for each subject, as described below, based on the subject's condition (the percentage of blasts in the peripheral blood and bone marrow, and peripheral blood cell counts) at the completion of Course 1.

- 1) Has blasts in the peripheral blood: Subject will proceed to Course 2 without delay and receive SGI-110 for 10 days.

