- 2) No blasts in the peripheral blood: The percentage of blasts in the bone marrow will be assessed.
  - a) The percentage of blasts in the bone marrow is  $\geq 5\%$ : Subject will proceed to Course 2 without delay and receive SGI-110 for 10 days.
  - b) The percentage of blasts in the bone marrow is  $< 5\%$ : The neutrophil and platelet counts in the peripheral blood will be assessed.
    - i) The neutrophil count is  $\geq 500/\mu\text{L}$  and platelet count is  $\geq 50000/\mu\text{L}$ : Subject will proceed to Course 2 without delay and receive SGI-110 for 5 days.
    - ii) The neutrophil count is  $< 500/\mu\text{L}$  or platelet count is  $< 50000/\mu\text{L}$ : Transition to Course 2 will be postponed, and the subject's peripheral blood will be assessed at least once a week. After that, if the subject has no blasts in the peripheral blood but the neutrophil and platelet counts are recovered to  $\geq 500/\mu\text{L}$  and  $\geq 50000/\mu\text{L}$ , respectively, he/she will proceed to Course 2 and receive SGI-110 for 5 days. If blasts are found in the subject's peripheral blood while his/her transition to Course 2 is on hold, he/she will proceed to Course 2 and receive SGI-110 for 10 days. For subjects whose transition to Course 2 is on hold because blasts are not found in his/her peripheral blood and the neutrophil and platelet counts are  $< 500/\mu\text{L}$  and  $< 50000/\mu\text{L}$ , respectively, it is possible to proceed to Course 2 and receive SGI-110 for either 5 or 10 days at the discretion of the investigator or subinvestigator based on the benefit-risk balance for the subject.

SGI-110 diluent for reconstitution, 3 mL contains 3 mL of custom diluent for reconstitution in a 5-mL glass vial.

SGI-110 for injection, 100 mg vial and SGI-110 diluent for reconstitution, 3 mL should be stored at 2°C to 8°C and 2°C to 30°C, respectively, until use. Both vials are for single use only as they are free of preservatives.

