**7.1.4.2.7 Day 8, Day 15, and Day 22 of Course 2 (10-day regimen)**

The observations, examinations, and evaluations listed below will be conducted, and the dates of the conduct and data obtained will be documented in the medical records and CRF.

Clinical Symptoms	Subjective symptoms and objective findings
Vital Signs	Blood pressure (systolic/diastolic), pulse rate, and body temperature
Hematology Test	Hb, Hct, RBC count, WBC count, differential WBC count (visual count: blast cells [leukemia cells], lymphoblastoid cells, monoblasts, promyelocytes, myelocytes, metamyelocytes, segmented neutrophils, stab leucocytes, lymphocytes, eosinophils, monocytes, basophils, prolymphocytes, and promonocytes), platelet count, and reticulocytes

If peripheral blood testing indicates that the subject meets criteria for remission, or if clear disease progression is observed, bone marrow aspiration will be performed.

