**7.1.4.2.11 Day 8, Day 15, and Day 22 of Course 2 (5-day regimen)**

The observations, examinations, and evaluations listed below will be conducted, and the dates of the conduct and data obtained will be documented in the medical records and CRF.

Clinical Symptoms	Subjective symptoms and objective findings
Vital Signs	Blood pressure (systolic/diastolic), pulse rate, and body temperature
Hematology Test	Hb, Hct, RBC count, WBC count, differential WBC count (visual count: blast cells [leukemia cells], lymphoblastoid cells, monoblasts, promyelocytes, myelocytes, metamyelocytes, segmented neutrophils, stab leucocytes, lymphocytes, eosinophils, monocytes, basophils, prolymphocytes, and promonocytes), platelet count, and reticulocytes

If peripheral blood testing indicates that the subject meets criteria for remission, or if clear disease progression is observed, bone marrow aspiration will be performed.

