9.3.1 Adverse Events

AEs will be coded using MedDRA version 20.0.

- The number of subjects and incidence will be summarized for all treatment-emergent AEs (TEAEs).
- The number of subjects and incidence will be summarized for all TEAEs by MedDRA SOC and PT.
- The number of subjects and incidence will be summarized for all TEAEs by MedDRA SOC, PT, and CTCAE grade. If a subject experiences the same TEAE 2 or more times, the most severe grade occurrence will be used for the analysis.
- The number of subjects and incidence will be summarized for all TEAEs by the timing of AE occurrence (in course 1, in or after course 2, and overall), MedDRA SOC and PT. AEs which had occurred in Course 1 and continued beyond course 2 will be included in “in or after course 2” category.

- TEAEs that DLTs and correspond to DLTs (preferred term) which were observed in course 1, in or after course 2, and overall will be tabulated (number of subjects and incidence rate). AEs which had occurred in Course 1 and continued beyond course 2 will be included in “in or after course 2” category.

Adverse drug reactions (TEAEs for which a causal relationship with the IMP are suspected adverse reaction) will be summarized in the same manner as above.

9.3.2 Death, Other Serious Adverse Events, CTCAE Grade 3 or above Adverse Events, and Other Significant Adverse Events

The following TEAEs will be summarized in the same manner as in first bullet of [Section 9.3.1 Adverse Events](#). Also the following TEAEs, excluding TEAEs of grade ≥ 3 , will be summarized in the same manner as in second bullet of [Section 9.3.1 Adverse Events](#).

- Serious TEAEs
- TEAEs leading to death
- TEAEs leading to discontinuation in course 1, in or after course 2, and overall
- TEAEs of grade ≥ 3
- TEAEs leading to postponement of the start of the next course
- TEAEs leading to skipping of IMP administration

Adverse drug reactions (TEAEs for which a causal relationship with the IMP are suspected adverse reaction) will be summarized in the same manner as above.

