9.3.3 Clinical Laboratory Tests

The following items will be tabulated by cohort and overall (Cohorts 1, 2, and 4) for hematological and biochemical tests performed at each time point.

- Descriptive statistics of the measured values
- Descriptive statistics of the change from baseline
- Shift tables comparing the baseline grade with last grade, worst grade through all courses and worst grade of each course categorized by CTCAE grade
- Shift tables comparing the baseline values with last value, worst value through all courses and worst value of each course by using the normality judgment (high, normal, low)

If the laboratory test parameter has both upper limit of normal and lower limit of normal, larger difference one from median of normal range will be taken as worst value.

The following item will be tabulated by cohort and overall (Cohorts 1, 2, and 4) for the urinalysis.

- Shift tables comparing the baseline values with last value, worst value through all courses and worst value of each course.

Also, some of laboratory test parameter will be figured by subject performed at each time point of course 1 and all courses.

- Line plots will be used to assess hemoglobin, red blood cell, white blood cell, neutrophil, lymphocytes and platelet.

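### Cohort 3's adverse event category after Course 1, and its Course 2 time-point tables, mix 10-day and 5-day courses, and no planned table shows how many subjects had each

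*Protocol*

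**What the plan says.** Protocol 6.1 gives Cohort 3 ten days of dosing in Course 1 and then dosing "for 10 or 5 days in Course 2 (Extended treatment period), for 5 days in Course 3 and subsequent courses". The Course 2 choice rests on "the percentage of blasts in the peripheral blood and bone marrow, and peripheral blood cell counts" when Course 1 ends:

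- Blasts in the blood, or at least 5% in the marrow, lead to 10 days.
- Marrow blasts below 5% with neutrophils of at least 500/µL and platelets of at least 50,000/µL lead to 5 days.
- Subjects with lower counts are held. Some of them may "receive SGI-110 for either 5 or 10 days at the discretion of the investigator or subinvestigator based on the benefit-risk balance for the subject".

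Section 7.1.4.2.4 places this decision at Day 29 of Course 1, where "it will be assessed when to start Course 2 and which regimen (10-day regimen or 5-day regimen) to use". Two separate Course 2 schedules follow: sections 7.1.4.2.5 to 7.1.4.2.8 for 10 days and 7.1.4.2.9 to 7.1.4.2.12 for 5 days.

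SAP section 9 runs the safety analyses by cohort, with a combined group for Cohorts 1, 2 and 4. In SAP 9.3.1 adverse events are summarised "by the timing of AE occurrence (in course 1, in or after course 2, and overall), MedDRA SOC and PT", and persisting Course 1 events are also counted in the later category. SAP 9.3.3 gives descriptive statistics "for hematological and biochemical tests performed at each time point", and SAP 9.3.4 does the same for vital signs. SAP 9.1 counts administrations in Course 1 only. For later courses it gives the number of subjects dosed and the number of courses per subject.

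**The concern.** Protocol 1.2.3 says that Cohort 3 was reinstated to learn how Japanese patients tolerate 60 mg/m² for 10 days before a phase 3 trial. Course 2 is the only place where a repeated 10-day course can be observed. In the planned tables it shares a column with 5-day Course 2 and with all later 5-day courses.

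The mixing weights are not fixed by design. They depend on who still has blasts after Course 1, so the later Cohort 3 column can change between two sets of subjects although toxicity under each regimen is the same. For laboratory and vital-sign data, one visit label also stands for two different times since dosing.

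**Working it through.** **1. Dose per course.** Protocol 1.2.3 gives 300 mg/m² per course for 60 mg/m² over 5 days, and 60 × 5 = 300 reproduces it. The 10-day course is 60 × 10 = 600 mg/m². The ratio is 300/600 = 0.50, so a 5-day course is half the course dose at the same daily dose.

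**2. Time since last dose in Course 2.** The last dose falls on Day 12 (10-day) or Day 5 (5-day). The visit windows are those in the Cohort 3 schedules of events.

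| Visit | 10-day regimen | 5-day regimen |
|---|---|---|
| Day 15 | window 13–18: 1 to 6 days | window 12–18: 7 to 13 days |
| Day 22 | window 19–25: 7 to 13 days | window 19–25: 14 to 20 days |

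The two ranges do not overlap at either visit. This affects haematology and vital signs; biochemistry is not scheduled on these two days.

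**3. What the adverse event category contains.** For Cohort 3 it holds 10-day Course 2, 5-day Course 2, 5-day Course 3 onward, and carried-over Course 1 events. After Course 1 a subject has at most one 10-day course. With c courses in total, the 10-day share of later courses is therefore at most 1/(c − 1): 100% at c = 2, 50% at c = 3, 33% at c = 4. Protocol 11.3.1.2 planned adverse events for each course. SAP 9.3.1 is coarser, and SAP section 13 does not list this as a change.

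**4. Can the mix be recovered?** Not from the planned tables. Administrations are counted for Course 1 only (SAP 9.1), compliance is marked not applicable (SAP 8.2.1), and by-subject listings lie outside the SAP (section 1).

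**5. Illustration with assumed rates.** Suppose six subjects start Course 2, k of them on 10 days, with event rates of 50% (10-day) and 20% (5-day). Neither rate comes from the documents. The pooled rate is (k × 50% + (6 − k) × 20%)/6.

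- k = 1: (50 + 100)/6 = 25%
- k = 3: (150 + 60)/6 = 35%
- k = 5: (250 + 20)/6 = 45%

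Conversely, with three subjects on each regimen, a pooled 2/6 fits 10-day and 5-day counts of 0/3 and 2/3, 1/3 and 1/3, or 2/3 and 0/3.

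**6. Which split is plausible?** The 5-day branch is close to composite remission. Protocol 1.2.2.1.1.2 reports this in 8 of 50 relapsed or refractory subjects (16%), and 6 × 0.16 = 0.96, or about one of six. That points nearer to 5/1 than to 3/3. However, the 16% comes from 5-day dosing, and Protocol 6.1 says that remission came sooner with 10 days. It is also not a rate at the end of Course 1. Fewer than six may reach Course 2: in the reference study 67% and 78% received two cycles, which is 4.0 and 4.7 of six.

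**The case against.** The strongest reply is that the question put to Cohort 3 is answered in Course 1. Tolerability is judged by DLTs in that course, when every subject is on 10 days, and adverse events in Course 1 have their own column. No MTD is determined for Cohort 3, no decision rule uses its later data, and no tests or intervals are planned. All of this stands. A reader might infer that the primary tolerability result is blended with half-dose data; the documents do not support that.

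Nor is all safety information after Course 1 merged. Worst laboratory grade is shown for each course, transfusions and dosed subjects are tabulated per course, and time-point tables identify the course. Course 3 onward can therefore be separated there. Six haematology parameters are also plotted by subject over all courses, although the SAP does not say that the plots will identify the regimen.

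It can also be argued that by-cohort tables describe the strategy as assigned, which the protocol states openly. That justifies keeping a pooled column. It does not supply the missing count on each regimen, and it does not make a pooled Day 15 mean interpretable.

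Finally, a split would compare persistent disease with marrow clearance in a handful of subjects. This is correct. A reader might take the split columns as the toxicity attributable to each regimen, and they cannot be read that way.

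**Conclusion.** The point holds as a reporting weakness in secondary safety tables for Cohort 3. It covers the adverse event category after Course 1, the Course 2 time-point summaries of laboratory values and vital signs, and the missing count of subjects on each Course 2 regimen. The two-fold difference in course dose and the non-overlapping days since last dose follow directly from the documents.

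The size of the distortion is unknown. Under the assumed rates above, the pooled figure lies 15 points from each regimen at a 3/3 split, but 5 points from the 10-day rate at 5/1. A reader might infer a large bias from the even split. The documents give no basis for that split or for those rates, and the only documented remission rate points elsewhere. This is a worthwhile, low-cost improvement and does not threaten the trial's main conclusion.

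**What to change.** For Cohort 3 only:

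1. In SAP 9.1, tabulate the number of IMP administrations for every course, so that the Course 2 split is visible.
2. In SAP 9.3.1, show adverse events separately for Course 2 given over 10 days, Course 2 given over 5 days, and Course 3 onward, each with its own number treated. Say where carried-over Course 1 events are counted. Keep the pooled column and label it 'mixed regimens'.
3. In SAP 9.3.3 and 9.3.4, present Course 2 time-point data by regimen received.
4. State that the split is descriptive, non-randomised and confounded by disease status.

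The cost is SAP wording and a few table columns, some of which may hold only one to three subjects. No new data are needed: Protocol 7.2.6 already has the date, time and dose of each administration recorded in the CRF during the primary evaluation part.

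Separately, Protocol 3.5, item 1, rules out a change of dose or regimen within a subject, while 6.1 provides for one in Cohort 3. The two passages should be reconciled.

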**7.1.4.2.5 Day 1 of Course 2 (10-day regimen)**

If written informed consent is obtained for extended treatment, the observations, examinations, and evaluations listed below will be conducted before the start of IMP administration on Day 1 of Course 2, and the dates of the conduct and data obtained will be documented in the medical records and CRF. If measurement of vital signs and body weight, hematology test, blood biochemistry test, and urinalysis have been completed within 4 days before Day 1, the available data can be used instead.

Clinical Symptoms	Subjective symptoms and objective findings
Viral Test a	HBV-DNA
Vital Signs	Blood pressure (systolic/diastolic), pulse rate, and body temperature
Body Weight b	Body weight
Hematology Test	Hb, Hct, RBC count, WBC count, differential WBC count (visual count: blast cells [leukemia cells], lymphoblastoid cells, monoblasts, promyelocytes, myelocytes, metamyelocytes, segmented neutrophils, stab leucocytes, lymphocytes, eosinophils, monocytes, basophils, prolymphocytes, and promonocytes), platelet count, and reticulocytes
Blood Biochemistry Test	AST (GOT), ALT (GPT), ALP, LDH, TP, ALB, T-Bil, BUN, UA, Cr, blood glucose (fasting), Ca, Mg, Na, K, and Cl
Urinalysis	Bilirubin, occult blood, protein, and urobilinogen

If peripheral blood testing indicates that the subject meets criteria for remission, or if clear disease progression is observed, bone marrow aspiration will be performed.

a A viral test will be performed only in subjects who are found to be either HBcAB or HBsAB positive at screening.

b Body weight will be measured and the dose of IMP to be administered will be determined according to the calculation of BSA.

**7.1.4.2.6 Day 2 to Day 5 and Day 9 to Day 12 of Course 2 (10-day regimen)**

The observations, examinations, and evaluations listed below will be conducted before the start of IMP administration, and the dates of the conduct and data obtained will be documented in the medical records and CRF.

Clinical Symptoms	Subjective symptoms and objective findings
Vital Signs	Blood pressure (systolic/diastolic), pulse rate, and body temperature

If peripheral blood testing indicates that the subject meets criteria for remission, or if clear disease progression is observed, bone marrow aspiration will be performed.

**7.1.4.2.7 Day 8, Day 15, and Day 22 of Course 2 (10-day regimen)**

The observations, examinations, and evaluations listed below will be conducted, and the dates of the conduct and data obtained will be documented in the medical records and CRF.

Clinical Symptoms	Subjective symptoms and objective findings
Vital Signs	Blood pressure (systolic/diastolic), pulse rate, and body temperature
Hematology Test	Hb, Hct, RBC count, WBC count, differential WBC count (visual count: blast cells [leukemia cells], lymphoblastoid cells, monoblasts, promyelocytes, myelocytes, metamyelocytes, segmented neutrophils, stab leucocytes, lymphocytes, eosinophils, monocytes, basophils, prolymphocytes, and promonocytes), platelet count, and reticulocytes

If peripheral blood testing indicates that the subject meets criteria for remission, or if clear disease progression is observed, bone marrow aspiration will be performed.

